#### 10.2.2 UNANTICIPATED PROBLEMS

Unexpected Events (UE) will be recorded on the UE/SAE log (Appendix D) and will include information such as the date of the event, when the study team was informed of this event, details of the event, when the IRB was notified, and whether the SAE form was completed. The IRB will be notified of each UE that may occur during the study.

The Office for Human Research Protections (OHRP) considers unanticipated problems involving risks to participants or others to include, in general, any incident, experience, or outcome that meets all of the following criteria:

- unexpected (in terms of nature, severity, or frequency) given (a) the research procedures that are described in the protocol-related documents, such as the IRB-approved research protocol and informed consent document; and (b) the characteristics of the participant population being studied;
- related or possibly related to participation in the research (in the guidance document, possibly related means there is a reasonable possibility that the incident, experience, or outcome may have been caused by the procedures involved in the research); and
- suggests that the research places participants or others at a greater risk of harm (including physical, psychological, economic, or social harm) than was previously known or recognized.

If an UE occurs the IRB will be notified and the study will be adjusted as needed to protect the health and safety of the participants. Depending on the nature of the UE, the research protocol, inclusion/exclusion criteria, and informed consent will be changed to reflect the possibility of this event reoccurring. During this time, no new participants will be recruited and the research procedures for currently enrolled participants will be stopped. Each UE will be recorded and reported throughout the study.

### 10.3 REPORTING PROCEDURES

We will be adopting the following table for reporting procedures:

What Event is Reported	When is Event Reported	By Whom the Event is Reported	To Whom the Event is Reported
Fatal or life-threatening unexpected, suspected serious adverse reactions	Within 24 hours of initial receipt of information	Investigator	Local/internal IRBs
Non-fatal, non-life threatening unexpected, suspected serious adverse reactions	Within 10 working days of initial receipt of information	Researcher	Local/internal IRBs/Institutional Officials, DSMB
Unanticipated adverse device effects	Within 10 working days of investigator first learning of effect	Investigator	Local/internal IRBs
Unanticipated problem that is not an SAE	Within 10 working days of the investigator becoming aware of the problem	Investigator	Local/internal IRBs/Institutional officials
All Unanticipated Problems	Within 30 working days of the IRB's receipt of the report of the UP from the investigator	IRB	OHRP
		Investigator	External IRBs

CONFIDENTIAL

---

#### 11.3.1 REPORTING OF PREGNANCY

Pregnancy tests will be administered on the first session of the experiment to all women of child-bearing potential (CBP). After testing negative, the experiment can continue. On subsequent sessions, female participants will be asked if it is possible that they may have become pregnant since the previous session. If the participant responds yes, or is unsure, then a pregnancy test will be administered. Within the study target population (ages 18-35), menstruating females, regardless of age are considered "CBP". Women who have had a hysterectomy or a bilateral oophorectomy are not considered of "CBP". There are no studies that suggest TMS would interfere with pregnancy. However, should a participant become pregnant during the study, her participation will be immediately terminated.

### 10.4 TYPES AND DURATION OF FOLLOW-UP OF PARTICIPANTS AFTER ADVERSE EVENTS

Medical monitors and PI will follow up with participants within ten working days of an SAE that is related to stimulation.

## 11 STATISTICAL PLAN

The statistician for this study is [name].

### 11.1 STATISTICAL ANALYSIS STRATEGIES

The statistical analysis plan below aligns with the aims that are described in Section 2.3. all statistical estimates of population parameters will be tabulated along with corresponding confidence intervals (CIs) to convey levels of precision / imprecision. All hypothesis tests that yield large p-values ( $p>0.05$ ) will be reported as being inconclusive.

*Phase One* overarching goal: Investigate the causal role of frontal theta and parietal alpha oscillations in the prioritization and suppression of working memory representations. To control for non-specific effects of rhythmic TMS, we will use an active control: arrhythmic TMS (randomized inter-pulse-interval) that is matched to the target stimulation in number of pulses and temporal duration. All analyses will be performed on the difference from condition-matched arrhythmic TMS. The key analyses are built upon a three-way parallel arms design: with factors TMS frequency (theta versus alpha), location (frontal versus parietal), and cue direction (left versus right retro-cue). There is an equal number of trials for each of these conditions and there are 75 trials for each condition per participant.

Aim 1 (primary outcome): Stimulation that is aligned to the endogenous activity of the brain (frontal theta and parietal alpha) is hypothesized to improve performance whereas the mismatched frequency of stimulation is hypothesized to decrease performance (frontal alpha and parietal theta). Performance is assessed using Pashler's working memory capacity metric ( $k$ ) which is defined as:  $k = N * \frac{HR*FA}{1-FA}$  where  $N$  is the number of the items that are held in memory. HR is the hit rate defined as the percent correct for trials where the probe does not match the encoding array. FA is the false alarm rate defined as the percent incorrect for trials where the probe does match the encoding array. We will perform a two-way repeated-measures ANOVA with two within-participant factors TMS site (frontal or parietal) and TMS frequency (theta or alpha). We expect to observe a small p-value ( $p < 0.05$ ) for the interaction between TMS site and TMS frequency. Post-hoc t-tests will be performed using Tukey's method to control for multiple comparisons. *Sensitivity analysis*: In addition to calculating changes in working memory capacity, the impact on hit rate, false alarm rate, and overall accuracy will be calculated. The robustness of these effects will be estimated using an individual differences analyses where baseline performance is used as a covariate to improve model estimation. Finally, the titration of working memory load by participant will be added as a covariate to explore if this factor changes the model estimation. These are framed as exploratory analyses.

Aim 2 (primary outcome): Stimulation is hypothesized to increase the targeted frequency of stimulation relative to arrhythmic stimulation. This aim will provide evidence of target engagement, i.e. that stimulation is effective at modulating the targeted rhythm. Using Morlet wavelet convolution, the amplitude of theta and alpha oscillations will be estimated during task performance. The average across trials for each conditions will be calculated and baseline corrected using decibels to the time before the encoding array (700 to 300 milliseconds). Then, the average amplitude within the individual theta (ITF  $+$ /- 1 Hz) and alpha frequency (IAF  $+$ /- 1 Hz) band will be calculated for the second half of the train of TMS pulses. Previous research has shown that amplitude increase from stimulation increases over the course of the TMS train. Frontal-theta and parietal-alpha amplitude values will be submitted to a two-way repeated-measures ANOVA with TMS frequency by TMS site. We hypothesize to find a significant interaction ( $p < 0.05$ ) between TMS site and TMS frequency such that theta amplitude in frontal cortex increases greater for TMS to frontal in theta frequency and alpha amplitude in parietal cortex increases greater for TMS to parietal cortex in alpha frequency. Post-hoc t-tests will be performed using Tukey's method to control for multiple comparisons. *Sensitivity analysis*: To understand the specificity of this effect, the time-course for the impact of stimulation of amplitude will be plotted as well as the topographic plot for our effects. Cluster analysis will be used to estimate the spread of our effect in time and space. These analyses provide evidence to the robustness of the

impact of stimulation on amplitude.

**Aim 3 (secondary outcome):** Theta and alpha oscillations are hypothesized to play antagonistic roles whereby theta oscillations are associated with an increase in neural excitability and alpha oscillations are associated with a decrease in neural excitability. Therefore, we will investigate the impact of stimulation on the other frequency band. Theta stimulation is hypothesized to decrease the amplitude of alpha oscillations and alpha stimulation is hypothesized to decrease theta oscillations. This method is identical for that of Aim 2 except that the values submitted to the ANOVA are instead frontal-alpha and parietal-theta amplitude values. We hypothesize to find a significant interaction ( $p < 0.05$ ) between TMS site and TMS frequency such that alpha amplitude decrease is greater for TMS to frontal in theta frequency and theta amplitude decrease is greater for TMS to parietal cortex in alpha frequency. Post-hoc t-tests will be performed using Tukey's method to control for multiple comparisons. *Sensitivity analysis:* Similar to the sensitivity analysis of Aim 2, the time-course and topographic plots with cluster analysis will quantify the spread of these effects. Furthermore, an exploratory theta-alpha antagonism metric (theta amplitude minus alpha amplitude within the site of interest) will be used to quantify a shift in the relative distribution of theta and alpha amplitude.

**Aim 4 (secondary outcome):** Theta oscillations in frontal cortex are hypothesized to play a causal role in precision of working memory representations. During the probe, the participant responds with a specific color from a comprehensive color wheel. Plus or minus 15 degrees around the color wheel is considered "correct." For the correct trials, the precision is calculated as the distance in degrees from the response of the participant to the actual color of the memory item. To investigate if theta oscillations play a causal role in precision, the impact of theta stimulation on precision relative to arrhythmic and as a function of visual field will be investigated using a two-way repeated-measures ANOVA: TMS frequency (theta or alpha) and visual field (left and right) for stimulation to frontal cortex. We hypothesize to find an interaction between TMS frequency and visual field such that precision is increased when theta stimulation is applied to the frontal cortex with a retro-cue to the contralateral visual field (right visual field). Post-hoc t-tests will be performed using Tukey's method to control for multiple comparisons. *Sensitivity analysis:* To better understand the impact of stimulation on precision, we will include additional covariates such as the location in the color space and the accuracy for the participant across color space. It is possible that participants will have differences in sensitivity to color changes dependent on the color, so this control analyses accounts for those differences.

**Aim 5 (secondary outcome):** Stimulation that is aligned to the endogenous activity of the brain is hypothesized to entrain neural activity. Inter-trial phase coherence (ITPC) quantifies alignment of neural oscillations across trials. Stimulation in frontal-theta and parietal-alpha is proposed to increase ITPC in a frequency specific manner relative to control stimulation. A similar method for extracting instantaneous phase is used as that used to extract instantaneous amplitude (Aim 2). ITPC is calculated as the average phase angle in complex space of unit vectors across trials, then taking the magnitude of the resulting vector. These ITPC values are then averaged for the second half of the TMS train as described in (Aim 2). Frontal-theta and parietal-alpha ITPC values will be submitted to a two-way repeated-measures ANOVA with TMS frequency by TMS site. We hypothesize to find a significant interaction ( $p < 0.05$ ) between TMS site and TMS frequency such that theta ITPC in frontal cortex increases greater for TMS to frontal in theta frequency and alpha ITPC in parietal cortex increases greater for TMS to parietal cortex in alpha frequency. Post-hoc t-tests will be performed using Tukey's method to control for multiple comparisons. *Sensitivity analysis:* Similar to the sensitivity analysis of Aim 2, the time-course and topographic plots with cluster analysis will quantify the spread of these effects.

**Phase Two Overarching Goal:** Investigate the causal role of in-phase theta-frequency between frontal and parietal cortex in the prioritization and suppression of working memory representations. To control for non-specific effects of dual-site rhythmic TMS, we will use an active control: arrhythmic TMS (randomized inter-pulse-interval). Two

forms of arrhythmic stimulation are used: arrhythmic-in-synchrony stimulation delivers simultaneous stimulation to the two sites, but there is no consistent frequency component to the stimulation. Thus, activity in the two sites may be synchronized but not in a frequency-specific manner. The second control condition for stimulation is arrhythmic-independent where two trains of TMS are delivered in random patterns. There is no synchronization between the two pulse trains. Arrhythmic-independent controls for frequency and synchrony specificity of stimulation. All analyses will be performed on the difference from condition-matched arrhythmic TMS (in-phase minus arrhythmic-in-synchrony and anti-phase minus arrhythmic-independent). The key analyses are built upon a three-way design: with factors TMS frequency (theta and alpha), TMS alignment (in-phase and anti-phase), and cue direction (left and right retro-cue).

**Aim 6 (primary outcome):** Stimulation that is delivered in-phase to frontal and parietal cortex in the theta frequency is hypothesized to increased working memory capacity relative to anti-phase theta stimulation. Working memory capacity is quantified using Pashler's metric (see Aim 1). We will perform a two-way repeated-measures ANOVA with a between participants factor of TMS frequency (theta and alpha) and within-participants factor of TMS alignment (in-phase and anti-phase). We hypothesize to find a significant interaction ( $p < 0.05$ ) between TMS frequency and TMS alignment such that in-phase TMS in theta-frequency increases working memory capacity. Post-hoc t-tests will be performed using Tukey's method to control for multiple comparisons. *Sensitivity analysis:* Similar to aim 1, the impact of stimulation on hit rate, false alarm rate, and overall accuracy will be calculated. The robustness of these effects will be estimated using an individual differences analyses where baseline performance is used as a covariate to improve model estimation. Finally, the titration of working memory load by participant will be added as a covariate to explore if this factor changes the model estimation. These are framed as exploratory analyses.

**Aim 7 (primary outcome):** Stimulation that is delivered in-phase to frontal and parietal cortex in theta frequency is hypothesized to increase functional connectivity between the regions in a frequency specific manner. Functional connectivity will be measured using weighted phase lag index (WPLI). To calculate WPLI, first Morlet wavelet convolution is performed to extract instantaneous phase and amplitude for the frequency of interest for the two target sites. Next, the cross-spectral density is calculated (one signal multiplied by the complex conjugate of the other). From the cross-spectral density the imaginary component of the resulting signal is extracted. Then those imaginary values are averaged over the time frame of instance (here, the second half of the stimulation train). Finally, the magnitude of the resulting vector is taken to be the WPLI. This metric quantifies the consistency of phase lag between the two target regions and is weighted towards signals with a 90 or 270 degree offset to address a common confound in EEG, volume conduction. We hypothesize that in-phase theta-frequency stimulation will increase theta-frequency WPLI strength between frontal and parietal cortex. In addition, we hypothesize that in-phase theta frequency stimulation will increase WPLI magnitude for retro-cues to the right visual field greater than the increase for stimulation with a retro-cue to the left visual field. This hypothesis is motivated by the finding that the left hemisphere processes information for the contralateral visual hemifield and that theta oscillations are linked to the active processing of information. Using a two-way ANOVA with factors for TMS frequency (theta or alpha) and retro-cue direction (left or right), we hypothesize a significant interaction ( $p < 0.05$ ) between TMS frequency and retro-cue direction such that WPLI magnitude is the greatest for theta-frequency stimulation with a retro-cue to the right visual field. Post-hoc t-tests will be performed using Tukey's method to control for multiple comparisons. *Sensitivity analysis:* The frequency, topographic, and spatial specificity of these effects will be explored. Similar to Aim 2, the time-course of WPLI can be estimated using a sliding window to demonstrate if functional connectivity rises and peaks at the end of the stimulation train. Furthermore, the topographic increase in functional connectivity will be quantified across the scalp to see if the effect is specific to the targeted regions. Finally, the frequency specificity will be explored by calculating functional connectivity across the full spectral range (2-30 Hz) and the specificity of connectivity changes in frequency domain will be displayed. Together, these analyses will establish the robustness

of our a priori effect. Furthermore, these confirmatory sensitivity analyses avoid the multiple comparisons problem by relying on the initially established analyses.

**Aim 8 (secondary outcome):** Stimulation that is delivered in-phase is hypothesized to decrease the relative phase difference (phase lag) between the frontal and parietal cortex, whereas anti-phase stimulation is hypothesized to increase the phase lag. If stimulation entrained neural activity directly to the stimulation train, then this pattern of phase lag differences would be expected (because in-phase stimulation is delivered with zero phase lag and anti-phase stimulation is delivered with a phase lag). To calculate phase lag, first Morlet wavelet convolution is performed to extract instantaneous phase and amplitude for the frequency of interest for the two target sites. Next, the cross-spectral density is calculated (one signal multiplied by the complex conjugate of the other). From the cross-spectral density the phase angle is extracted, this is the phase lag. Then those phase lag values are averaged over the time frame of instance (here, the second half of the stimulation train). Finally, the angle of the resulting vector is taken to be the average phase lag. This metric quantifies the degrees of phase lag between the two target regions. Using a two-way ANOVA with factors for TMS frequency (theta or alpha) and TMS alignment (in-phase or anti-phase), we hypothesize a significant main effect ( $p < 0.05$ ) of TMS alignment such that phase lag is different between in-phase and anti-phase where in-phase decreases the phase lag and anti-phase increases the phase lag. We also hypothesize that this effect will be strongest for theta-frequency stimulation, which is hypothesized to be revealed as a significant main effect between TMS frequency and TMS alignment. Post-hoc t-tests will be performed using Tukey's method to control for multiple comparisons. *Sensitivity analysis:* Similar to Aim 7, the spread of stimulation effects in time, space, and frequency will be explored.

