Aim 4 (secondary outcome): Theta oscillations in frontal cortex are hypothesized to play a causal role in precision of working memory representations. During the probe, the participant responds with a specific color from a comprehensive color wheel. Plus or minus 15 degrees around the color wheel is considered "correct." For the correct trials, the precision is calculated as the distance in degrees from the response of the participant to the actual color of the memory item. To investigate if theta oscillations play a causal role in precision, the impact of theta stimulation on precision relative to arrhythmic and as a function of visual field will be investigated.

Aim 5 (secondary outcome): Stimulation that is aligned to the endogenous activity of the brain is hypothesized to entrain neural activity. Inter-trial phase coherence (ITPC) quantifies alignment of neural oscillations across trials. Stimulation in frontal-theta and parietal-alpha is proposed to increase ITPC in a frequency specific manner relative to control stimulation.

*Phase Two Overarching Goal:* Investigate the causal role of in-phase theta-frequency between frontal and parietal cortex in the prioritization and suppression of working memory representations.

Aim 6 (primary outcome): Stimulation that is delivered in-phase to frontal and parietal cortex in the theta frequency is hypothesized to increased working memory capacity relative to anti-phase theta stimulation. Working memory capacity is quantified using Pashler's metric.

Aim 7 (primary outcome): Stimulation that is delivered in-phase to frontal and parietal cortex in theta frequency is hypothesized to increase functional connectivity between the regions in a frequency specific manner. Functional connectivity will be measured using weighted phase lag index. In addition, we hypothesize that in-phase theta frequency stimulation will increase WPLI magnitude for retro-cues to the right visual field greater than the increase for stimulation with a retro-cue to the left visual field. This hypothesis is motivated by the finding that the left hemisphere processes information for the contralateral visual hemifield and that theta oscillations are linked to the active processing of information.

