#### 6.5.2 RETRO-CUE WORKING MEMORY TASK

The retro-cue working memory task consists of five epochs. In the first epoch, the participant is presented with lateralized stimuli, colored squares, in both the left and right visual hemifield. The participant is given one second to encode these items into memory. During the screening participants will be presented with one, two, or three colored squares in both visual fields, and in subsequent session there is a fixed number of stimuli. In the second epoch, there is a one second delay period over which the iconic memory of the colored squares decays. In the third epoch, the participant is presented with an informative retro-cue, an arrow to the left or right, that is 100% predictive of the upcoming probe, or an uninformative neural cue, an arrow pointing in both directions. In the fourth epoch, participants must maintain the items in memory over a two second delay. It is during this epoch, after the presentation of the retro-cue that TMS is delivered in sessions four and five. Finally, in the probe epoch participants are presented with a dotted outline of the squares on the left or the right and solid lines around the item to be recalled. At the center of the screen is a color wheel and a blank square. Participants move a joystick towards the direction of the color in the color wheel that they wish to select. The square in the center changes color to match the selected color by the participant. Once the color is selected, the participant pulls the trigger on the joystick with their index finger. Participants are instructed to be both fast and accurate.

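### Primary working-memory score k (Aims 1 and 6) is defined on match and non-match probes, but the only retro-cue task described is colour-wheel report, so k cannot be computed as written

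*Combined protocol and SAP*

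**What the plan says.** Section 11.1, Aim 1, names Pashler's k as the performance measure and defines its two ingredients: "HR is the hit rate defined as the percent correct for trials where the probe does not match the encoding array", and "FA is the false alarm rate defined as the percent incorrect for trials where the probe does match the encoding array". Aim 6, the primary behavioural aim of phase two, takes its definition of k from Aim 1. In both aims, hit rate, false-alarm rate and overall accuracy appear only as sensitivity analyses, closed by the sentence "These are framed as exploratory analyses".

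Section 6.5.2 describes the probe differently. The item to be recalled is outlined, and "At the center of the screen is a color wheel and a blank square". Then: "Participants move a joystick towards the direction of the color in the color wheel that they wish to select". Section 2.3, Aim 4, agrees: "During the probe, the participant responds with a specific color from a comprehensive color wheel". So does section 11.1 under Aim 4, which adds the scoring rule: "Plus or minus 15 degrees around the color wheel is considered" correct.

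**The concern.** The hit and false-alarm rates in Aim 1 need a displayed probe colour and a judgement of whether it matches memory. The described task has neither, so the primary score and the task do not fit together, and section 11.1 disagrees with itself between Aim 1 and Aim 4.

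This is the primary behavioural score of both phases, and section 4.1 says that no blinding is attempted. If the wheel was used, some other score must replace k, and the documents do not say which. Candidate wheel scores measure different things. A threshold score, such as the proportion within 15 degrees, rises when more items are remembered and also when remembered items are reported more precisely. Aim 4 separately predicts that "precision is increased when theta stimulation is applied to the frontal cortex with a retro-cue to the contralateral visual field". On a threshold score, a precision effect could therefore appear as the capacity effect of Aim 1.

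**Working it through.** **1. The plan's own figure.** Section 11.2 gives effect size 0.532, 95% power and 48 participants. Treat 0.532 as the standardised mean of a within-participant contrast, two-sided 5% (sidedness is not stated). The normal approximation gives ((1.960 + 1.645)/0.532)² = 45.9, so 46. The noncentral t gives 48, with power 0.9505. The figure reproduces, but it is an effect on working-memory capacity as scored in the earlier study.

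**2. What k needs and what the task supplies.**

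| Needed for k (11.1, Aim 1) | Supplied (6.5.2; Aim 4 in 2.3 and 11.1) |
|---|---|
| Probe colour that matches or does not match | Blank square and colour wheel |
| Match or non-match judgement | Continuous colour selection by joystick |
| Trials of each probe type | 600/8 = 75 per phase-one condition, split by stimulation type and cue side only |
| Two rates, HR and FA | One accuracy figure, within 15 degrees |

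As described there are 0 match and 0 non-match trials, so both rates have a zero denominator. The perception task (6.5.1) and the session 2 colour-wheel precision task (5.2) are not described as match/non-match tasks either.

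**3. What the wheel can give.** The correct window is 30 of 360 degrees, so uniform guessing succeeds 30/360 = 1/12 of the time. With p the proportion correct, a guess-corrected score is N(p − 1/12)/(11/12). Over the 60–85% titration range of section 4 this is 0.56–0.84 (N = 1), 1.13–1.67 (N = 2) and 1.69–2.51 (N = 3). The documents define no such score.

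**4. Why the replacement matters.** Assume a memory rate of 0.9 and N = 3 (the rate is not in the documents). With response SD 12 degrees, a remembered item falls within 15 degrees with probability 0.790, so p = 0.9 × 0.790 + 0.1/12 = 0.719 and the guess-corrected score is 2.08. With SD 10 degrees the probability is 0.867, p = 0.788 and the score is 2.31. Mixture-model capacity is 3 × 0.9 = 2.70 in both cases.

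**5. Simulation, illustrative only.** The test is the Aim 1 site-by-frequency interaction, rhythmic minus arrhythmic, with site within participant, 48 participants and 75 × 2 = 150 trials per cell. Assumed: memory rate about 0.9, SD about 12 degrees, N = 1, 2 or 3 equally likely. Extra variation means added cell-to-cell variation in precision and memory rate. Entries are the percentage of datasets with two-sided p < 0.05.

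| Frontal-theta effect | Proportion | Guess-corrected | N × mixture rate |
|---|---|---|---|
| None | 4 | 5 | 5 |
| SD 12 to 10, both cue sides | 98 | 98 | 5 |
| Same, extra variation | 75 | 70 | 3 |
| SD 12 to 11, both cue sides | 56 | 51 | 5 |
| SD 12 to 10, right cue only | 61 | 50 | 4 |
| Same, extra variation | 28 | 27 | 5 |
| SD 12 to 11, right cue only* | 13 | 16 | 4 |
| Same, extra variation* | 6 | 6 | 4 |
| Memory rate +0.03 | 25 | 21 | 64 |
| Same, extra variation** | 14 | 13 | 39 |

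Each row has 500 datasets (Monte Carlo SE at most 2.2 points), except *200 and **150 (SE up to about 4 points). Allowing for this noise across repeated runs, the mixture score rejects in about 1–7% under a precision-only effect. The memory gain is detected in about 11–30% on the threshold scores and about 36–64% on the mixture score.

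Proportion and guess-corrected score gave the same decision in all 500 datasets when N was equal, because one is a linear function of the other at fixed N. When N differs between participants, as section 4 says it will, they can disagree in up to about 15% of datasets.

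**6. The printed operator.** The text reads HR*FA. With N = 2 and HR = 0.8 that form gives 0.40 at FA = 0.2 and 0 at FA = 0. A minus sign gives 1.50 and 1.60. The asterisk may be a misread minus, and the point does not depend on it.

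**The case against.** The textual conflict is hard to dispute. The objections concern how much follows from it.

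- *The defect may lie only in the task description.* Section 11.2 says that the earlier study used the present task and reported working-memory capacity. If match/non-match probes were run, k is computable, subject to the operator check, and 6.5.2 and the Aim 4 text are wrong. This stands as a possibility, but one side must still be corrected.
- *The 15-degree rule already gives a score.* It gives accuracy, not a false-alarm rate. Accuracy is listed only as exploratory for Aims 1 and 6, so promoting it changes the primary endpoint.
- *The simulation measures a choice of score, not the contradiction.* This stands. No section mentions a mixture model, and the rates, SDs and effects are all assumed. The 98% row is a favourable corner: its standardised interaction effect is about 0.64, above the 0.532 behind the sample size, and it acts on both cue sides, whereas Aim 4 predicts the right. The smallest case shown is close to the null rate. Aim 4 also analyses precision separately, so a precision effect would not go wholly unseen.

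A reader might infer that the trial can yield no primary behavioural result, or that a score has been or will be picked after seeing results. The documents support neither. Wheel data would still give accuracy, and match/non-match data would give k. Lack of blinding does not show selection, and the documents do not say whether outcomes by condition have been seen.

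**Conclusion.** The point holds and must be fixed before the primary analysis. The primary score in Aims 1 and 6 cannot be computed from the described task, and the hit-rate and false-alarm sensitivity analyses fail with it. That conclusion rests on the text alone.

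The effect on results is conditional. Under the stated assumptions, a precision-only effect reaches significance on a threshold score in about 6% to 98% of datasets, depending on its size, the cue sides affected and the extra variation, against about 1–7% on a mixture score. These figures show that the choice can matter; they do not predict this trial's result. Nor can the choice between raw proportion and its guess-corrected form be dismissed as immaterial, since the two can disagree when N varies.

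**What to change.** Issue a dated amendment that reconciles 6.5.2 with 11.1 according to the task actually run.

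- **If the colour wheel was used:** replace k in Aims 1 and 6 with one named score. Examples are the proportion within 15 degrees, which is the documents' own correctness rule, or N(p − 1/12)/(11/12). Fix one in advance. Drop the hit-rate and false-alarm analyses, state whether N counts the cued side or both, and report a mixture-model memory rate as a named sensitivity analysis.
- **If match/non-match probes were used:** correct 6.5.2 and the Aim 4 text, state the number of trials of each type, and use N(HR − FA)/(1 − FA).
- **Either way:** check the operator on the source page. Section 1.5 dates version 7.0 to September 2025; if outcomes by condition have already been seen, label the score post hoc.

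The cost is an amendment and re-coding of one score, with no new data. Two downsides should be stated. A threshold score mixes capacity with precision, and a mixture fit in each cell brings its own distributional assumptions. Carrying the 0.532 effect behind 48 participants over to a redefined score is also an assumption.
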